#### 9. RESEARCH METHODS

#### 9.1. Study design

This is a NI, observational, retrospective cohort study utilizing a nested case-control design with secondary data collection. The broader cohort for this study is the Optum EHR database during the proposed study period of 01 January 2010 to most recent available at the time of start of data

[figure not shown]
collection (31 March 2023). This study period has been chosen to reflect the most current and complete data in the Optum database, with sufficient baseline time to examine risk factors for patients with myocarditis in each of the cohorts with index dates of 2016-later.

**Figure 1** summarizes the overall study design. Among the overall Optum EHR study population, the following mutually exclusive cohorts and index dates will be defined to address the study objectives:

- Cohort 1 Post-mRNA COVID-19 vaccination myocarditis cohort: first date of a
  myocarditis diagnosis code within 21 days after vaccination from 11 December 2020 to most
  recent data available, allowing for at least 30 days pre or post index myocarditis diagnosis for
  medical notes to confirm diagnosis through end of study period.
- Cohort 2 Post-SARS-CoV-2 infection myocarditis: first date of a myocarditis diagnosis code within 8 weeks after a positive SARS-CoV-2 test from 01 January 2020 to most recent data available, allowing for at least 30 days pre or post index myocarditis diagnosis for medical notes to confirm diagnosis through end of study period.
- Cohort 3 Pre-COVID myocarditis: most recent date of a myocarditis diagnosis from 01 January 2016 to 01 November 2019, allowing for at least 30 days pre or post index myocarditis diagnosis for medical notes to confirm diagnosis through end of study period.
- Controls for the multivariable risk factor analysis, a random sample of matched patients
  without myocarditis will be selected, e.g. with an encounter date within the same month as
  the index date for the myocarditis case, and with a similar amount of follow-up time from
  entry into the cohort and activity in the database. Additional matching criteria may be
  determined, and details of the matching methods and appropriate modeling considerations
  will be provided in the SAP.

Additional details on index dates and episode definitions will be provided in the SAP.

Figure 1. Study Design

- Censored at minimum of myocarditis diagnosis, death, disenrollment, or end of the study period

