# **Myocarditis cases:**

- 2. Diagnosis of myocarditis identified using ICD codes in EHR and/or claims when available. (ICD codes will be provided in the SAP)
- 3. At least one myocarditis inpatient record or two myocarditis records of any type dated greater than or equal to 30 days apart
- 4. Myocarditis diagnosis date between 01 January 2016 most recent EHR data available (31 March 2023)
- 5. At least 365 days of enrollment or activity in the EHR prior to the index myocarditis diagnosis.

Myocarditis cases meeting the above criteria will be divided into the following three cohorts with their own unique inclusion criteria:

- a) Cohort 1 Post- mRNA COVID-19 vaccine myocarditis cases:
  - 1. Myocarditis diagnosis date 11 December 2020 or later
  - 2. Record of mRNA vaccination within 21 days prior to the myocarditis diagnosis without a record of SARS-CoV-2 positive test within 8 weeks prior to myocarditis diagnosis
  - 3. Availability of medical notes to use for confirmation of myocarditis post-mRNA COVID-19 vaccination thirty days before or after the index event
- b) Cohort 2 Post- SARS-CoV-2 infection myocarditis cases:
  - 1. Myocarditis diagnosis date 01 January 2020 or later
  - 2. Record of SARS-CoV-2 positive test within 8 weeks prior to myocarditis diagnosis, with no record of mRNA COVID-19 vaccination during that time
  - 3. Availability of medical notes to use for confirmation of myocarditis post-SARS-CoV-2 infection thirty days before or after the index event
- c) Cohort 3 Pre-COVID-19-era acute/viral myocarditis cases:
  - 1. Most recent Myocarditis diagnosis date prior to 01 November 2019
  - 2. Availability of medical notes to use for confirmation of myocarditis within thirty days before or after the index event

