#### 9.2.2. Exclusion criteria

Patients meeting any of the following criteria will not be included in the study:

1. Less than 365 days between the first recorded date a patient had activity of any kind recorded the Optum EHR database and a patients first recorded ICD code of myocarditis based on the cohort criteria above, or the index date for the controls.

Relevant codes/operational criteria for this study will be documented in an SAP, which will be dated, filed and maintained by the sponsor.

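### Cohort 3 is indexed at the latest myocarditis code, while Cohorts 1 and 2 use the first, so in repeat-coded cases consequences of the disease can enter as risk factors

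*Protocol*

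**What the plan says.** **Index rules.** Section 9.1 indexes Cohort 3 at the "most recent date of a myocarditis diagnosis from 01 January 2016 to 01 November 2019". The Abstract repeats this, and Section 9.2.1(c) gives it as "Most recent Myocarditis diagnosis date prior to 01 November 2019". Cohort 2 is indexed at the "first date of a myocarditis diagnosis code within 8 weeks after a positive SARS-CoV-2 test". Cohort 1 is worded the same way, with a 21-day window after vaccination.

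**Who qualifies as a case (9.2.1).** "At least one myocarditis inpatient record or two myocarditis records of any type dated greater than or equal to 30 days apart".

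**What is measured before index.** Table 1 takes comorbidities, treatments, procedures and laboratory tests before the diagnosis or index date, and healthcare use in the preceding 6 months. For cases the index is the date of the qualifying diagnosis. No row leaves out time after an earlier myocarditis code.

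**Notes for validation (9.2.1(c)).** "Availability of medical notes to use for confirmation of myocarditis within thirty days before or after the index event".

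**Other anchors.** The 365-day exclusion in Section 9.2.2 runs to "a patients first recorded ICD code of myocarditis based on the cohort criteria above". Table 1 counts time to and since diagnosis from the first myocarditis diagnosis. The Figure 1 notes say follow-up is "Censored at minimum of myocarditis diagnosis, death, disenrollment, or end of the study period". Controls must be free of myocarditis before their index date; no such condition is set for Cohort 3 cases.

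**The concern.** A risk-factor analysis needs its covariates measured before disease onset. When the index is the latest code, everything between the first and latest codes counts as history. For myocarditis that interval is where heart failure, cardiac drugs, imaging and cardiology visits caused by the disease would be recorded. Table 1 names cardiac conditions, cardiac treatments and cardiac procedures among its examples, so these are variables the models would test.

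Two comparisons are at stake. The primary objective compares risk factors across the three cohorts, and a secondary objective compares PPV across them. If index, look-back and notes window mean one thing in Cohort 3 and another in Cohorts 1 and 2, a difference between cohorts cannot be separated from the difference in rule. Cohort 3 is also by far the largest: about 7,200 of 240 + 1,730 + 7,200 = 9,170 feasibility cases, or 79% (Section 9.5).

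**Working it through.** The Protocol gives no figure for this point and no sample-size derivation, so there is nothing to reproduce. The check is date logic plus an illustration.

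**1. How far can the index move?**
- One inpatient record and no other code: first and latest coincide, so the shift is 0 days.
- Qualifying by two records, both within the period: the latest code is at least 30 days after the first, by construction.
- Inpatient case with later follow-up codes: shifted by whatever the gap is.
- Maximum within the window, 01 January 2016 to 01 November 2019: 366 + 365 + 365 + 304 = 1,400 days, about 3.8 years.

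**2. What falls into the baseline?** Take a patient admitted with acute myocarditis and coded again 60 days later. The index is day 60. The admission, its drugs and its procedures precede the index, and the admission lies inside the 6-month healthcare-use window.

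**3. Does the notes window reach the first code?** With a window of 30 days either side of the latest code, a first code 30 days earlier is on the edge; at 31 days or more it is outside. For two-record cases the first code is therefore at best on the boundary.

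**4. Illustration of bias.** Let p0 be the prevalence of a condition before the first code, equal in cases and controls (true OR 1); f the share of cases indexed after their first code; and q the share of those who acquire the condition between first and latest code. Then

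p1 = p0 + (1 − p0) × f × q

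OR = [p1/(1 − p1)] / [p0/(1 − p0)]

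The Protocol gives none of p0, f or q; all are assumptions. At p0 = 5%:

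| f | q | p1 | OR |
|---|---|---|---|
| 10% | 10% | 0.0595 | 1.20 |
| 10% | 30% | 0.0785 | 1.62 |
| 30% | 10% | 0.0785 | 1.62 |
| 30% | 30% | 0.1355 | 2.98 |
| 50% | 10% | 0.0975 | 2.05 |
| 50% | 30% | 0.1925 | 4.53 |

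Over the same f and q, the range is 1.51 to 9.82 at p0 = 2% and 1.10 to 2.76 at p0 = 10%. With the index at first onset, f = 0 and the OR is 1.00. The formula ignores matching and adjustment, and assumes that controls do not acquire the condition over the same interval.

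**The case against.** **The SAP may deal with it.** Section 9.1 leaves further index-date and episode details to the SAP, as it does the code list and covariate definitions. An acute-only code list, an episode rule or a lag before index could limit the carry-over. That stands as a reason not to treat the harm as certain in size. It does not remove the point: the choice of the latest code is already fixed in three places without a stated reason, and details added to that rule do not reverse it.

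**The Protocol does not strictly contradict itself.** A reader might infer that the first-code anchors in Section 9.2.2 and Table 1 make the index rule self-contradictory. They do not. A patient with 365 days before the first code also has 365 days before the latest, and Table 1 may define time to first diagnosis alongside a separate index date. The Figure 1 note says only myocarditis diagnosis, without saying which one. The anchors are out of line with each other, which is a weaker statement.

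**The effect could be read as larger than it is.** Setting f = 1 with p0 = 5% gives odds ratios of 2.05, 3.22 and 6.00 for q of 5%, 10% and 20%. That assumes every Cohort 3 case is indexed late, which cannot be so where a single inpatient record qualifies.

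**Validation.** A reader might conclude that the notes window misses the acute episode and that the Cohort 3 PPV is therefore understated. Neither is shown. Later notes may restate earlier findings, a latest code may be a true recurrence, and only a sample of Cohort 3 is validated. Section 9.9 does, however, concede that a code may record a past event, and a latest-code rule makes such records more likely to be chosen.

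**Conclusion.** The point holds for Cohort 3 cases with more than one myocarditis code. As written, the rule places time after first onset in their baseline, and nothing in Table 1 takes it out. The shift is certain for two-record cases within the period, possible for inpatient cases with later codes, and absent for single-record cases. For conditions that follow from myocarditis, the bias in the odds ratio is upward. Even a true recurrence leaves the earlier disease in the baseline.

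The size is unknown, because the share of repeat-coded cases is not stated. The range of 1.20 to 4.53 is an illustration resting on the assumed p0, f and q, not an estimate for this study. A missed acute episode and a lower Cohort 3 PPV are possible consequences only. The rule should be changed before the cohorts are compared, since both cross-cohort comparisons depend on it.

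**What to change.** In the Abstract, Section 9.1 and Section 9.2.1(c), define the Cohort 3 index as the first myocarditis code from 01 January 2016 to 01 November 2019 in patients with no earlier recorded myocarditis code. The second half is needed: the study period starts in 2010, so the first code from 2016 alone would still admit patients coded in 2010–2015. Anchor the covariate look-back, control matching and 30-day notes window on that date. This also gives Cohort 3 cases the same freedom from prior myocarditis that controls must have. The text should say whether the no-earlier-code condition applies to Cohorts 1 and 2 as well, since Section 9.2.1 does not state one for them.

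The cost is a protocol amendment, re-deriving and re-matching Cohort 3, re-pulling and re-reviewing notes for its validation sample, and some loss from the roughly 7,200 cases; the Protocol gives no basis for estimating how much. The amendment log already records vendor delays in adjudication and control construction, and data collection is planned to end on 30 May 2025, so the timing matters.

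If re-adjudication is not feasible, the minimum is to end the covariate windows before the first recorded code and to run the Cohort 3 risk-factor models with first-code indexing as a sensitivity analysis. That limits the risk-factor bias but leaves the PPV comparison on unequal notes windows, which the report should then state.

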## 9.2. Setting

This study will use the US-based Optum's deidentified Electronic Health Record (EHR) data, with supplemental linkage to Optum's Integrated Claims-Clinical adjudicated claims dataset for those patients in the EHR who also have claims data available. For a subset of patients in the EHR, data exist including patient electronic clinical notes which will allow manual clinician review at Optum to confirm myocarditis cases based on available data that align with the Brighton Collaboration criteria. Review of clinical notes will not be conducted for the random sample of patients without evidence of myocarditis that will serve as controls for the risk factor analysis. Optum's role, processes, and data is described in more detail in Section 9.4.

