#### 9.2.1. Inclusion criteria

Patients must meet all of the following criteria to be eligible for inclusion in the study:

1. All ages

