# Controls for risk factor analysis:

- 1. Medical encounter and during the same month as their matched myocarditis case (index date for control select date closest to matched myocarditis case if ≥1 date/encounters are present)
- 2. At least 365 days of enrollment or activity in the EHR prior to index
- 3. No evidence of myocarditis prior to the index date
- 4. Details of matching criteria will be provided in the SAP

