#### 9.3. Variables

As described above, patients in the myocarditis cohorts will be identified via ICD codes in the EHR data, and a subset will be confirmed using Brighton Collaboration criteria  and medical record review. The main study variables of interest, including demographics, diagnostic, therapeutic and laboratory/examinations are listed in **Table 1: Variables and associated roles.** Operational definitions, codes, more detailed listings of comorbidities, procedures and treatments, as well as any additional variables will be provided in the SAP.

Table 1. Variables and Associated Roles (Detailed Operationalization to be Described in SAP)

Variable	Role
Year of birth	Demographic
Sex	Demographic
Race/Ethnicity	Demographic
Geographic region (census regions)	Demographic
Payer type	Demographic
Date of matched encounter (index date for controls)	Index
Date of qualifying myocarditis diagnosis (index date for cases)	Diagnosis and index
Age at time of diagnosis (e.g., index date, or if unavailable then age entered or calculated in database closest to myocarditis diagnosis)	Diagnosis

Variable	Role
Time to diagnosis (time from first Optum EHR record until first myocarditis diagnosis date)	Diagnosis
Time since diagnosis (time from first myocarditis diagnosis date until last date in the Optum EHR or date of death)	Diagnosis
Laboratory biomarkers if feasible (e.g. troponin, CRP, CK-MB, CPK, additional lab markers TBD)	Diagnosis
Imaging* (e.g. echocardiogram, Cardiac MRI, Cardiac Magnetic Resonance, cMR, ECG)	Diagnosis
Procedures* (Biopsy / cardiac biopsy)	Diagnosis
mRNA COVID-19 vaccination	Exposure
SARS-CoV-2 infection	Exposure
Medical comorbidities prior to diagnosis/index date** (e.g. Charlson categories, Feudtner Complex chronic conditions [CCC] for pediatric populations, Healthcare Cost and Utilization Project Clinical Classifications Software [HCUP CCS] groups, incl. cardiac, immune, inflammatory conditions)	Medical history
Treatments prior to diagnosis/index date* (e.g. prior cardiac or COVID-related treatments, frequency of other drug classes)	Medical history
Procedures prior to diagnosis/index date* (e.g. cardiac, HCUP CCS groups)	Medical history
Labs of interest prior to diagnosis/index date* (e.g. labs mentioned above, as well as other cardiac labs, basic metabolic panel, complete blood count, urinalysis, thyroid test, lipid panel, cultures)	Medical history

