## 9.7. Data analysis

# **Primary objective**

In primary analyses, descriptive statistics will be presented to characterize myocarditis patients in terms of demographic and clinical characteristics (including clinical characteristics of the myocarditis episode, as well as clinical history of the patient) as of the index date (date of myocarditis diagnosis code for myocarditis cases, or matched month/year among the control group). Specific demographics and clinical characteristics of interest are described in Section 9.3. Descriptive statistics will include counts and percentages for categorical data. For continuous variables, we will provide statistics such as mean, median, standard deviation, and range.

Additionally, appropriate statistical models such as conditional logistic regression or generalized estimating equations (GEE) incorporating non-independence of observations will be described in greater detail in the SAP. These models will estimate odds ratios (ORs) and 95% CIs of associations between demographics, clinical characteristics, and empirical model identified risk factors (based on either a stepwise selection approaches or via statistical significance in univariate models) and myocarditis. Models may incorporate laboratory based prognostic indices, severity status, clinical risk factors noted in Section 9.3 along with potential empirical model identified risk factors. These models will be run for the myocarditis cases and controls identified with ICD-10-CM codes in the EHR, and according to the inclusion and exclusion criteria as provided in Section 9.2, as well as for the cases that are validated by clinician reviews as myocarditis using the available Brighton Collaboration Criteria and information in medical record notes, as specified in Section 9.6. Model parameters will be detailed in the SAP.

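### Clinical notes near index are required of every case but of no control, so cases and controls can come from different source populations

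*Protocol*

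**What the plan says.** Section 9.2.1 introduces its list with "Patients must meet all of the following criteria to be eligible for inclusion in the study". Each case cohort then has its own notes criterion:

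- Cohort 1: "Availability of medical notes to use for confirmation of myocarditis post-mRNA COVID-19 vaccination thirty days before or after the index event"
- Cohort 2: "Availability of medical notes to use for confirmation of myocarditis post-SARS-CoV-2 infection thirty days before or after the index event"
- Cohort 3: "Availability of medical notes to use for confirmation of myocarditis within thirty days before or after the index event"

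Controls need an encounter in the same month as their case, no earlier myocarditis, and "At least 365 days of enrollment or activity in the EHR prior to index". Notes are not mentioned, and Section 9.2 says that control notes will not be reviewed.

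Section 9.2 also limits where notes exist: "For a subset of patients in the EHR, data exist including patient electronic clinical notes". Section 9.6 says that only some EHR systems supply them. Section 9.4 describes a database fed by more than 57 sources.

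Section 9.7 runs the models on code-identified cases "according to the inclusion and exclusion criteria as provided in Section 9.2, as well as for the cases that are validated" by clinicians. On matching, the notes to Figure 1 list IDN among example factors and defer the final criteria to the SAP. Neither the design text of Section 9.1 nor the control criteria name IDN.

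Section 9.6 describes the validation workflow differently from Section 9.2.1. There, the vendor's text-processing team establishes whether notes exist for patients who already qualify: all of them in Cohorts 1 and 2, and random samples of the pre-2020 cases.

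**The concern.** A nested case-control comparison needs controls from the population that would have supplied the cases. Under the stated rules, a patient with coded myocarditis in a system that supplies no notes cannot become a case, but a patient without myocarditis in that system can become a control. Selection into the analysis then depends jointly on case status and on system.

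Systems may differ in race, payer mix, region, coding intensity and completeness of comorbidity recording. These are the kinds of variable that the study examines as risk factors. A difference between systems could therefore be read as a difference between people who do and do not develop myocarditis. Section 9.7 also allows empirical risk factors to be chosen by stepwise selection or univariate significance, so an association of this kind could be selected into the model.

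The order of steps matters as well. If notes are part of qualification (Section 9.2.1), the code-based case set is restricted to patients with notes. If availability is checked after qualification (Section 9.6), it is not. The two sections define different case sets for the primary models.

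**Working it through.** The protocol states no sample size, power, alpha or control ratio, so there is no figure of its own to reproduce. The check has two parts.

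**Eligibility rules side by side**

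| Requirement | Cases | Controls |
|---|---|---|
| At least 365 days of prior enrollment or activity | yes | yes |
| Notes within 30 days of index | yes, all three cohorts | no |
| Possible source | note-contributing systems only | whole database |

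**Size of a spurious odds ratio (illustration)**

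All of these inputs are assumptions, because the protocol gives none of them:

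- p1 is the prevalence of the factor in note-contributing systems, and p0 is its prevalence elsewhere.
- f is the share of eligible controls who are in note-contributing systems.
- The true odds ratio is 1, and there is no matching on or adjustment for system.

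Cases all come from note-contributing systems, so their prevalence is p1. Control prevalence is pc = f·p1 + (1 − f)·p0. The expected odds ratio is [p1/(1 − p1)] / [pc/(1 − pc)].

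For p1 = 0.20, p0 = 0.15 and f = 0.5:

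- pc = 0.5 × 0.20 + 0.5 × 0.15 = 0.175
- case odds = 0.20/0.80 = 0.250
- control odds = 0.175/0.825 = 0.212
- odds ratio = 0.250/0.212 = 1.18

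Other values:

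| p1 vs p0 | f = 0.3 | f = 0.5 | f = 0.7 | f = 0.9 |
|---|---|---|---|---|
| 20% vs 20% | 1.00 | 1.00 | 1.00 | 1.00 |
| 20% vs 15% | 1.27 | 1.18 | 1.10 | 1.03 |
| 20% vs 10% | 1.67 | 1.42 | 1.22 | 1.07 |

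The bias can go either way. With 15% in note-contributing systems, 20% elsewhere and f = 0.5, the odds ratio is (0.15/0.85)/(0.175/0.825) = 0.176/0.212 = 0.83.

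**Chance of a false finding**

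This uses an unmatched Wald test at two-sided 5%, 4 controls per case (assumed), the 20% vs 15% scenario at f = 0.5, and the feasibility counts in Section 9.5 as numbers of cases. For n = 240:

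- SE = √[1/48 + 1/192 + 1/168 + 1/792] = 0.182
- ln 1.18 = 0.164, so z = 0.164/0.182 = 0.90 and the chance of rejection is about 15%

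The same calculation gives about 68% for 1,730 cases and over 99% for 7,200. Section 9.5 does not say whether those counts were taken with the notes rule in force.

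**With system matching**

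If each case and its controls come from the same system, both have prevalence p1 and the expected odds ratio is odds(p1)/odds(p1) = 1.00. This removes only the between-system part. Within a system, cases must still have notes near index while controls need only an encounter.

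**The case against.** The strongest reply is that bias requires two further conditions: controls left unmatched and unadjusted for system, and a factor whose prevalence or recording differs between systems. Figure 1 names IDN as a possible matching factor, and the protocol properly leaves matching detail to a SAP that is not at hand. If the SAP fixes IDN, most of the between-system problem goes. This stands, and it is why the consequence is stated conditionally. It does not answer the eligibility rule itself, which is fixed in the protocol and applies to one side only. IDN matching may also be incomplete: the protocol ties notes to EHR systems and nowhere equates these with IDNs.

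Second, restricting cases to those that can be adjudicated is defensible, since Section 9.9 regards misdiagnosis as potentially high. That is fair. The restriction alone narrows the population without biasing an odds ratio; the bias comes from not restricting controls in the same way.

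Third, a reader might infer that Section 9.3, which says "a subset will be confirmed using Brighton Collaboration criteria", contradicts a notes requirement for all cases. It does not strictly do so. A case can have notes and still go unsampled (Cohort 3) or fail validation, so the coded-case and validated-case models remain distinct. The wording that does conflict is the order of steps in Section 9.6 against Section 9.2.1.

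Finally, the magnitudes rest wholly on assumed inputs. That also stands.

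**Conclusion.** The point holds in conditional form, with moderate confidence. The stated eligibility rules limit cases to note-contributing systems and leave controls unrestricted, and Section 9.7 carries this into the code-based models. Without matching on or adjustment for system, factors that differ between systems can show spurious odds ratios. In the 20% vs 15% illustration these run from 1.03 to 1.27 as f falls from 0.9 to 0.3, with 1.18 at f = 0.5. They are 1.00 under system matching or equal prevalence.

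A reader might go further and conclude that system differences will appear as risk factors. The protocol does not support that, because the final matching criteria are in the SAP and no figure on system differences is given. A reader might also conclude that the roughly 240 Cohort 1 cases will shrink. That cannot be established either, because Section 9.5 does not say whether they were counted before or after the notes rule.

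**What to change.** Choose one of two routes in Section 9.2.1:

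- (a) Remove note availability from the three cohorts' inclusion criteria and use it only to define the validation subset, meaning the PPV analysis and the validated-case model.
- (b) Keep it for cases, and add to the control criteria that controls come from the same note-contributing source and have notes available around their index date.

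Under either route, make IDN or note-contributing source a fixed matching factor for any model restricted to cases with notes. Reconcile Sections 9.2.1 and 9.6 on whether note availability is part of qualification or is checked afterwards.

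The cost is a wording change, re-extraction from data already held, re-matching of controls and model reruns. This is not trivial, since the amendment log already records vendor delays in adjudication and control construction. Route (a) also admits more unreviewed coded cases, which the planned validated-case model already addresses.
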